### 9.2.3 Termination Criteria

For patients who terminate the ABBVIE REGIMEN prematurely for whatever reason the EoT eCRF page should be filled in and the reason for treatment discontinuation should be documented. If the reason for ABBVIE REGIMEN discontinuation is due to an SAE, the event must be reported to AbbVie within 24 hours of physician awareness (see Section 11.5).

If, in such patients, there is evidence of virological response during therapy or at EoT, the SVR12 and SVR24 pages should be completed if respective data is available.

#### 9.2.4 Investigator Selection Criteria

University centers and outpatient clinics qualified by training and experience in the management of patients with CHC will be selected to participate in this study. The AbbVie Affiliate Medical Director will ensure that sites participating in the study are representative of the medical practice in the country, have the ability to conduct the study and their availability of the target patient population. The type of the participating treating institute will be documented in the eCRF.

## 9.3 Variables

### 9.3.1 Primary Variable

- The percentage of patients achieving SVR12 (HCV RNA <50 IU/mL 12 weeks [i.e. ≥70 days] after the last actual dose of the ABBVIE REGIMEN)

### 9.3.2 Secondary Variables

- Type of treatment regimen (± Dasabuvir, ± RBV, intended and actual combination, dose and duration)
- Adherence  
*A period of 7 days in a row of missed intake of the ABBVIE Regimen during the time between documented first dose and last dose will issue a medication error report.*
  - Percentage of the DAA dose taken in relation to the target dose of DAA (cumulative dose taken divided by target dose in percent)
  - Percentage of the RBV dose taken in relation to the target dose of RBV (cumulative dose taken divided by target dose in percent)
  - Percentage of missed RBV treatment days in relation to the target number of RBV treatment days
- PAM-13, BMQ, PSP satisfaction and utilization questionnaires
- Portal hypertension in cirrhotic patients as assessed by hepatic venous pressure gradient (HVPG) and/or clinical symptoms prior to treatment initiation, at EoT, as well as 12 and 24 weeks after EoT
- Resistant virus variants at post-baseline time points compared to baseline

## 9.4 Data Sources

Source documents are defined as original documents. The investigator will document patient data in his/her own patient files which will serve as source data for the study. Data are collected from the source documents for each patient in the study, consisting of medical records containing demographic data, medical, treatment and diagnostic documentation and laboratory assessments.

The investigator(s)/institution(s) will permit study-related monitoring, audits, independent ethics committee/- review board (IEC/IRB) review, and regulatory inspection(s), providing direct access to source data documents.

### 9.4.1 Data to be Documented

This observational study covers three documentation periods, see Figure 1. An overview on data to be collected throughout the study is summarized in **Table 2**.

---

Confidential Information

After the patient has signed an informed consent, the following data will be documented in the eCRF, if available from the patient charts based on assessments done in physicians' routine clinical practice.

#### **9.4.1.1 Inclusion Documentation**

The following will be documented:

- Demographic information
  - Interleukin 28B (IL28B) genotypes
- CHC disease characteristics
  - Year of diagnosis and mode of infection
  - Stage of liver fibrosis
- CHC treatment history
  - Naïve or experienced
  - If experienced, most recent prior therapy and outcome
- Relevant medical history, co-morbidities and co-infections
- Concomitant medication, see 9.4.1.5
- ABBVIE REGIMEN ± RBV

- **Laboratory data**

Key clinical chemistry	Remarks
▪ ALT (alanine-aminotransferase)	including upper limit of normal (ULN),
▪ AST (aspartate-aminotransferase)	including ULN, AST to platelet ratio index (APRI) and Fibrosis-4 Score/Index (FIB-4)* will be calculated
▪ γ-GT (gamma-glutamyltransferase)	
▪ Total bilirubin	
▪ Albumin	
▪ Creatinine	creatinine clearance # will be calculated
▪ AFP	
Key hematology	
▪ Hb (Hemoglobin)	
▪ Platelets	
▪ Prothrombin time	or international normalized ratio (INR)
Virology	
▪ HCV genotype and subtype	
▪ HCV RNA	quantitative/ qualitative HCV RNA by polymerase chain reaction (PCR) test, see 9.4.1.4
HIV-infected patients only	
▪ CD 4 count (cluster of differentiation 4)	most recent assessment
▪ HIV RNA	in copies/mL

\*derived from patient's age, ALT, AST and platelets

#by Cockcroft-Gault-Formula based on creatinine, gender, age and weight

- Data on portal hypertension (for patients with cirrhosis only): HVPG or clinical assessments (e.g. splenomegaly, presence of esophageal varices, gastric varices, surrogate lab markers, CT, MRI)
- Viral resistance (blood for viral sequencing)
- PAM-13, BMQ

#### **9.4.1.2 During Treatment Documentation**

Follow-up visits are scheduled by the physician per routine clinical practice. Likewise treatment, procedures and diagnostic methods will follow physicians' routine clinical practice.

The following will be documented:

- Laboratory data

Key clinical chemistry	Remarks
▪ ALT	including ULN
▪ AST	including ULN,
▪ γ-GT	APRI and FIB-4 will be calculated
▪ Total bilirubin	
▪ Creatinine	creatinine clearance will be calculated
Key hematology	
▪ Hb	
▪ Platelets	
Virology	
▪ HCV RNA	quantitative/ qualitative HCV RNA PCR test, see 9.4.1.4
HIV-infected patients only	
▪ CD 4 count	most recent assessment
▪ HIV RNA	in copies/mL

- Concomitant medication, see 9.4.1.5
- Adherence to ABBVIE REGIMEN ± RBV (ABBVIE REGIMEN - % of target dose taken and RBV Y/N)  
*A period of 7 days in a row of missed intake of the **ABBVIE Regimen** during the time between documented first dose and last dose will issue a medication error report.*
- Tolerability (sAEs and AEs, see 11.5) and pregnancies (see 11.6)
- Data on portal hypertension (for patients with cirrhosis only): HVPG or clinical assessments (e.g. splenomegaly, presence of esophageal varices, surrogate lab markers, CT, MRI) (EoT only)
- Viral resistance (blood for viral sequencing) (EoT only)
- PSP satisfaction and utilization questionnaires, PAM-13 and BMQ: only at EOT/premature discontinuation

#### **9.4.1.3 Post-Treatment Documentation**

Follow-up visits are scheduled by the physician per routine clinical practice. Likewise treatment, procedures and diagnostic methods will follow physicians' routine clinical practice.

---

Confidential Information

The following will be documented:

- Laboratory data

Key clinical chemistry	Remarks
▪ ALT	including ULN
▪ AST	including ULN,
▪ γ-GT	APRI and FIB-4, will be calculated
▪ Total bilirubin	
▪ Albumin	
▪ Creatinine	creatinine clearance will be calculated
Key hematology	
▪ Hb	
▪ Platelets	
▪ Prothrombin time	or INR
Virology	
▪ HCV RNA	quantitative/ qualitative HCV RNA PCR test, see 9.4.1.4
HIV-infected patients only	
▪ CD 4 count	most recent assessment
▪ HIV RNA	in copies/mL

- Tolerability (sAEs, see 11.4) and pregnancies (see 11.6)
- Data on portal hypertension (for patients with cirrhosis only): HVPG or clinical assessments (e.g. splenomegaly, presence of esophageal varices, surrogate lab markers, CT, MRI)
- Viral resistance (blood for viral sequencing)
- PSP Satisfaction and utilization questionnaires

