**Table 2 - Data Documentation Schedule**

Assessment/ Procedure (only available data to be collected; no diagnostic or monitoring procedures to be applied to the patients apart from those of routine clinical practice)	Baseline	Treatment Period			Post-treatment (PT) Period		
		On-treatment visits	Mid treatment visit for pts receiving 24 weeks of therapy	EoT b	Early PT visit	SVR 12 visit	SVR 24 visit
Informed consent	X a						
Demographic information	X						
IL28B	X						
Relevant CHC disease characteristics	X						
Liver fibrosis stage	X						
CHC treatment history	X						
HCV genotype and subtype	X						
HCV RNA samples	X	X	X	X	X	X	X
Clinical chemistry and hematology	X	X	X	X	X	X	X
ABBVIE REGIMEN initiation documentation	X						
ABBVIE REGIMEN adherence		X	X	X			
Concomitant medication	X	X	X	X			
Relevant medical history, co-morbidities	X						
sAE, AE and pregnancy reporting	X	X	X	X	X c	X d	X d
For patients receiving RBV: Evidence, in accordance with local label, that female patient or female partner of male patient is not pregnant	X						
Data on portal hypertension in patients with cirrhosis	X			X		X	X
Viral resistance sample	X			X		X	X
BMQ, PAM-13	X			X			
PSP evaluation		X	X	X	X	X	

Abbreviations: EoT = End of Treatment (at Week 12 or 24 or at premature discontinuation),  
PT = Post-Treatment

- a Written informed consent must be obtained before any data documentation in the eCRF
- b Patients who prematurely discontinue should return to the site to document EoT data
- c Tolerability documentation until PT week 4
- d Pregnancy reporting for patients treated with DAA plus RBV

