### **9.7.6 Tolerability Analysis**

All tolerability variables will be summarized using descriptive statistical methods for the SP stratified by type of combination treatment and scheduled treatment duration.

All SAEs, non-serious AEs and pregnancy occurrences are to be reported for patients included in the study (see Section 11.0 and 9.2.3). AEs will be coded using MedDRA.

The number and percentage of patients with treatment-emergent AEs (i.e. any reported event that begins or worsens in severity after initiation of study drug through 30 days post-study drug dosing) will be tabulated by primary MedDRA SOC and PT.

Corresponding summary tables will be provided for all serious treatment-emergent AEs.

The tabulation of the number of patients with treatment-emergent AEs by severity and relationship to study drug will also be provided. Patients reporting more than one AE for a given MedDRA PT will be counted only once for that term using the most severe incident for the severity summary table and the most related for the relationship summary table.

Patients reporting more than one type of event within a SOC will be counted only once for that SOC.

Additional details of the analysis of AEs will be specified in the SAP.

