## **11.4 Serious Adverse Event Collection Period**

SAEs will be reported to AbbVie from the time the physician obtains the patient's informed consent until 30 days or 5 half-lives following the intake of the last dose of physician-prescribed treatment.

---

Confidential Information

No use or disclose outside AbbVie is permitted without prior written authorization from AbbVie

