4.2.8.3 Adverse Events

All tolerability variables will be summarized using descriptive statistical methods for the SP stratified by treatment regimen and cirrhosis status and overall.

AEs will be coded using MedDRA. A glossary will show the verbatim terms and the corresponding coded terms used (see Table 12).

The number and percentage of patients with treatment-emergent AEs (i.e. any reported event that begins or worsens in severity after initiation of study drug through 30 days post-study drug dosing including those who are related to the study drug independent of the occurrence and those where the date of onset is missing) will be tabulated by primary MedDRA SOC and PT.

Corresponding summary tables will be provided for all serious treatment-emergent AEs and additional for all non-serious treatment-emergent AEs. In the table of non-serious AEs (that must exclude any SAE) only preferred terms that occurred at a frequency of $\geq 5\%$ in any treatment group will be displayed (no SOCs will be displayed).

The tabulation of the number of patients with treatment-emergent AEs by severity (AEs by severity [mild, moderate, severe], AEs leading to death, AEs leading to hospitalization) and relationship to study drug will also be provided (ABBVIE Regimen, ribavirin, medication error - paritaprevir/r-ombitasvir, medication error – dasabuvir, ABBVIE Regimen withdrawn, ribavirin withdrawn).

Patients reporting more than one AE for a given MedDRA PT will be counted only once for that term using the most severe incident for the severity summary table and the most related for the relationship summary table. Patients reporting more than one type of event within a SOC will be counted only once for that SOC.

The frequency of pregnancies will be displayed as well.

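### The rules for collecting non-serious adverse events after treatment contradict each other and do not match the 30-day treatment-emergent window used in the analysis

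*Protocol*

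**What the plan says.** **Analysis window.** Protocol section 9.7.6 defines a treatment-emergent AE as "any reported event that begins or worsens in severity after initiation of study drug through 30 days post-study drug dosing". SAP section 4.2.8.3 keeps that window and widens it, "including those who are related to the study drug independent of the occurrence and those where the date of onset is missing". The SAP also plans a separate table of non-serious treatment-emergent AEs, limited to preferred terms reaching 5% in any treatment group.

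**Collection rules.**
- During treatment (protocol 9.4.1.2): "Tolerability (sAEs and AEs, see 11.5) and pregnancies (see 11.6").
- After treatment (protocol 9.4.1.3): "Tolerability (sAEs, see 11.4) and pregnancies (see 11.6"). Non-serious AEs are no longer named, and the cross-reference moves from 11.5 (reporting of serious and non-serious events) to 11.4 (the collection period for serious events only).
- Protocol Table 2, copied into SAP section 4.2.2: the safety row covers serious AEs, AEs and pregnancy. At the early post-treatment visit it carries footnote c, "Tolerability documentation until PT week 4". At the SVR12 and SVR24 visits it carries footnote d, "Pregnancy reporting for patients treated with DAA plus RBV".
- Protocol 11.4: serious AEs are collected from consent "until 30 days or 5 half-lives following the intake of the last dose of physician-prescribed treatment".
- Protocol 11.5 and the general reporting sentence in 9.7.6: non-serious AEs are to be reported, under 11.5 through the eCRF. Neither gives an end date.

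**The concern.** A percentage of patients with a treatment-emergent event is only meaningful if events were sought over the whole period in which they are counted. Here the counting period is fixed at 30 days after the last dose, while the site instructions for non-serious events give three different answers: none after treatment (9.4.1.3), up to week 4 (Table 2), or no stated limit (9.7.6 and 11.5). A site reading 9.4.1.3 beside 9.4.1.2 could reasonably take the change of both the list and the cross-reference as a deliberate narrowing to serious events.

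At stake are the overall and the non-serious AE tables. The SAP makes tolerability a secondary objective (section 2) and lists serious and non-serious AEs among the secondary variables (4.1.2). If ascertainment after the last dose differs between sites, part of any difference in AE percentages between groups or against other studies may reflect which passage a site followed. Because the non-serious table has a 5% display threshold, an under-count could also remove a term from view.

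**Working it through.** The plan states no figure on this point, so there is none to reproduce. The check is a comparison of window lengths.

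**Inputs**
- Planned treatment of 12 or 24 weeks (protocol 9.2.2): 12 × 7 = 84 days, or 24 × 7 = 168 days.
- Post-dose part of the treatment-emergent window (protocol 9.7.6, SAP 4.2.8.3): 30 days.
- Non-serious AE coverage after the last dose under 9.4.1.3: 0 days.
- Non-serious AE coverage under Table 2 footnote c: to week 4. This is day 28 if weeks are simply counted (SAP Table 4 also puts it at 28 days), or day 29 as labelled in protocol Table 4.
- Serious AE coverage under the 30-day limb of 11.4: 30 days.

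**Formulas**
- Full window = treatment days + 30: 84 + 30 = 114 days; 168 + 30 = 198 days.
- Uncovered days = 30 − days covered after the last dose.
- Shares = uncovered days / 30, / 114 and / 198.

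**Results**

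| Rule followed | Uncovered days | Share of the 30 days | Share of 114 days | Share of 198 days |
|---|---|---|---|---|
| 9.4.1.3, non-serious AEs | 30 − 0 = 30 | 100% | 26.3% | 15.2% |
| Table 2, week 4 = day 28 | 30 − 28 = 2 | 6.7% | 1.8% | 1.0% |
| Table 2, week 4 = day 29 | 30 − 29 = 1 | 3.3% | 0.9% | 0.5% |
| 11.4, 30-day limb, serious AEs | 30 − 30 = 0 | 0% | 0% | 0% |

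The gap for non-serious events is therefore either the whole post-dose period or almost nothing, depending on the passage used. For 9.7.6 and 11.5 no gap can be calculated, because they set no end date. These are shares of calendar time. Turning them into missed events would need a post-treatment AE rate, which neither document gives.

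**The SAP addition.** SAP 4.2.8.3 also counts drug-related events whenever they occur. Apart from the open-ended reporting duty, no collection period corresponds to that part, and a 30-day rule would not cover it.

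**The case against.** The best case for the plan is that non-serious AEs are in fact requested after treatment. Section 9.4.1 presents Table 2 as the overview of data to be collected, and Table 2 marks AEs at the early post-treatment visit. Sections 9.7.6 and 11.5 require non-serious AEs to be reported, and 11.5 makes reporting event-driven through the eCRF and not tied to a visit. On that reading the shortfall is a day or two, and the missing-visit problem belongs to any non-interventional study that records only routine data, as section 9.9 acknowledges in general terms. This stands against any claim that the protocol asks only for serious events after treatment. It does not remove the conflict: 9.4.1.3 is the specific instruction for the post-treatment period, it omits non-serious AEs, and the general reporting duty sets no end date.

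Three stronger readings are tempting and are not supported:
- *Serious events are lost as well.* The line in 9.4.1.3 points to 11.4, whose first limb is 30 days, and 11.5 requires reporting within 24 hours of awareness. What remains is that 11.4 offers two alternatives without saying which governs.
- *About a quarter of events are missed.* The 26% and 15% are calendar time, and they apply only to a site following 9.4.1.3.
- *An early visit at day 15 leaves days 16 to 30 with no documentation point.* Days 15–56 in protocol Table 4 form an analysis window for laboratory results, which the SAP changes to days 8–56. They are not a visit schedule. Figure 1, which carries the collection windows, was not available for this check, and a visit after day 30 could still pick up earlier events.

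**Conclusion.** The plan is inconsistent as written and should be corrected. The defect concerns non-serious AEs: the uncovered time ranges from 1–2 days to all 30 days after the last dose according to which passage a site follows. The likely direction is an under-count of non-serious treatment-emergent AEs that varies by site. A reader might also infer that serious events will be over-represented. That could follow, but the documents do not establish it, because they give no post-treatment event rate and do not show how sites would resolve the conflict.

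The conclusion assumes that at least some sites would act on 9.4.1.3 as written, and that reports made under 9.7.6 and 11.5 would not fully make up the difference. Importance is moderate: safety is analysed descriptively, the protocol's own objectives do not list tolerability, and SVR12 is unaffected. The correction is cheap enough to be worth making.

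**What to change.** 1. In protocol 9.4.1.3, name serious and non-serious AEs with onset up to 30 days after the last dose, matching the window already stated in 9.7.6.
2. Change footnote c of protocol Table 2, and its copy in SAP section 4.2.2, from week 4 to the same 30 days.
3. Give 11.4 one unambiguous end date, reconciled with that window, and state the matching period for non-serious AEs in 11.5.
4. Add one eCRF prompt at the first routine visit on or after day 30, asking for AEs and serious AEs with onset in those 30 days.
5. In SAP 4.2.8.3, state that drug-related events after day 30 come only from spontaneous reports, or define how they are collected.

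With steps 1 to 4 the uncovered time by rule is 30 − 30 = 0 days for both kinds of event. The cost is wording and one eCRF question, with no extra visit or procedure. The drawback is some reliance on recall when the first such visit is the SVR12 visit. The SAP's SVR12 window opens at day 70, at least 70 − 30 = 40 days after the AE window has closed.

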**Table 2 - Data Documentation Schedule**

Assessment/ Procedure (only available data to be collected; no diagnostic or monitoring procedures to be applied to the patients apart from those of routine clinical practice)	Baseline	Treatment Period			Post-treatment (PT) Period		
		On-treatment visits	Mid treatment visit for pts receiving 24 weeks of therapy	EoT b	Early PT visit	SVR 12 visit	SVR 24 visit
Informed consent	X a						
Demographic information	X						
IL28B	X						
Relevant CHC disease characteristics	X						
Liver fibrosis stage	X						
CHC treatment history	X						
HCV genotype and subtype	X						
HCV RNA samples	X	X	X	X	X	X	X
Clinical chemistry and hematology	X	X	X	X	X	X	X
ABBVIE REGIMEN initiation documentation	X						
ABBVIE REGIMEN adherence		X	X	X			
Concomitant medication	X	X	X	X			
Relevant medical history, co-morbidities	X						
sAE, AE and pregnancy reporting	X	X	X	X	X c	X d	X d
For patients receiving RBV: Evidence, in accordance with local label, that female patient or female partner of male patient is not pregnant	X						
Data on portal hypertension in patients with cirrhosis	X			X		X	X
Viral resistance sample	X			X		X	X
BMQ, PAM-13	X			X			
PSP evaluation		X	X	X	X	X	

Abbreviations: EoT = End of Treatment (at Week 12 or 24 or at premature discontinuation),  
PT = Post-Treatment

- a Written informed consent must be obtained before any data documentation in the eCRF
- b Patients who prematurely discontinue should return to the site to document EoT data
- c Tolerability documentation until PT week 4
- d Pregnancy reporting for patients treated with DAA plus RBV

#### **9.4.1.4 HCV RNA Sample**

**HCV RNA sample** – the following needs to be documented:

- **Quantitative** HCV RNA by PCR test
  - Test name and result **in IU/mL**
  - Lower limit of detection (LLoD) **in IU/mL** and lower limit of quantification (LLoQ) **in IU/mL**
- **Qualitative** HCV RNA by PCR test
  - Test name and result **(positive/negative)**
  - LLoD **in IU/mL**

#### **9.4.1.5 Concomitant Medication**

**Concomitant medication** - the following will be documented:

- Concomitant medication used from the time when the decision is made to initiate treatment with the ABBVIE REGIMEN until after the last dose

It should be verified by the treating physician that concomitant medication can be safely administered with the ABBVIE REGIMEN (including ritonavir) and RBV. Some medications may be contra-indicated, some may require dose adjustments due to potential for drug-drug interactions (DDIs). The investigator or qualified designee should review the concomitant medication(s) labels and screen concomitant medications at each visit for potential DDIs.

#### **9.4.1.6 Standardized Assessment Tools**

##### Patient Activation Measure – (PAM-13)

PAM 13 is a measure used to assess the patient knowledge, skill, and confidence for self-management. It should require approximately 7 minutes to complete and is presented in Annex 1.

##### Beliefs Medication Questionnaire – (18-item BMQ)

The 18-item BMQ consists of 18 questions used to screen for patients' beliefs, attitudes and concerns about their medication.

---

Confidential Information

The BMQ should require approximately 10 minutes to complete and is presented in Annex 2.

